#### A RANDOMIZED, DOUBLE-BLIND, PLACEBO-CONTROLLED PHASE II STUDY OF OXYBUTYNIN VERSUS PLACEBO FOR THE TREATMENT OF HOT FLASHES IN MEN RECEIVING ANDROGEN DEPRIVATION THERAPY

#### **Eligibility Criteria (see Section 3.0)**

- Men who are currently receiving androgen deprivation therapy (ADT) for the treatment of prostate cancer. (See  $\S 3.2.1$ )
- Patients must be on a stable dose of all hormone-directed therapies for at least 28 days prior to registration. Patients receiving radiation therapy are eligible. (See §3.2.2)

None

**Required Initial Laboratory Values** 

- Eligible patient must have bothersome hot flashes for  $\geq 14$  days prior to registration. (See §3.2.3)
- No current or future planned use of any of the agents listed in Section 3.2.4 during the study period. (See §3.2.4)
- No current or prior use of oxybutynin as a treatment for hot flashes. (See  $\S3.2.5$ )
- Patients with a history of any of the contraindications to oxybutynin listed in Section 3.2.6 are not eligible. (See §3.2.6)
- IPSS score < 20 (See §3.2.8)
- Life expectancy of greater than 6 months. (See  $\S3.2.9$ )
- Age  $\geq$  18 years. (See §3.2.10)
- ECOG Performance Status 0, 1 or 2. (See §3.2.11)
- Participants must be able to speak and read English. (See  $\S3.2.12$ )

- \* **Days 1-7** of study will involve collection of BSD (Baseline Symptom Documentation). Study treatment is to be administered from Days **8-49**.
- \*\* The concentration of oxybutynin is 1 mg per 1 mL, so that placebos and active treatments will maintain blinding.
- \*\*\* Following 6 weeks of study treatment, the patient will be given the option of being unblinded (Section 8.3.2), and if he was on placebo, will be allowed to cross-over, be re-registered (See Section 4.7), receive either 2.5 or 5.0 mL of oxybutynin, equivalent to the amount of the placebo the patient had received prior to unblinding, for 6 weeks.

## Please refer to the full protocol text for a complete description of the eligibility criteria and treatment plan.

If the Group credited for enrollment is a non-Alliance Group, then other requirements from the credited Group may apply.

#### **1.0 BACKGROUND AND RATIONALE**

Therapies to decrease testosterone and other androgens are frequently utilized in men diagnosed with prostate cancer, and also in certain salivary gland tumors.[1, 2] Additionally, medications to block estrogen signaling are also commonly employed in men with estrogen and/or progesterone receptor positive breast cancer.[3] Although these therapies can have significant clinical efficacy, a rapid change in the circulating hormone levels can commonly cause patients to experience symptomatic hot flashes. Approximately 60-80% of prostate cancer patients being treated with either surgical (i.e. orchiectomy) or medical androgen deprivation therapy (ADT) will experience hot flashes.[4, 5] Hot flashes have been associated with negative impacts on patients' reported quality of life, fatigue, and sleep disturbance.[6-11] Additionally, patients with bothersome hot flashes may be less likely to complete the recommended course of ADT, which can negatively influence cancer prognosis. Given the prevalence of this symptom and the significance of associated toxicity, further study of potentially effective interventions is warranted.

#### 1.1 Treatment of Hot Flashes in Men

A variety of different therapies have been investigated for reducing hot flashes in men. Two progesterone analogs, megestrol and medoxyprogesterone, have randomized trial evidence demonstrating a significant reduction in hot flashes, with acceptable toxicity profiles.[12, 13] Both of these trials demonstrated that greater than 70% of patients receiving the study agents reported significant reductions in hot flashes. However, some oncologists are hesitant to prescribe these agents due to overexpression of progesterone receptors in a subset of patients with prostate cancer, and the uncertain clinical effects of these medication on oncologic outcomes.[14-16] Megestrol has also been associated with a decrease in prostate-specific antigen (PSA) after withdrawal suggesting some potential therapeutic effect by the drug.[17] Gabapentin, a gamma-aminobutyric acid analog, has also been shown to be effective at reducing hot flash frequency compared to placebo in men receiving ADT.[18] In that study, a dosedependent response to gabapentin was noted, with only patients receiving the highest dose (900 mg/day) demonstrating a statistically significant moderate improvement in hot flash scores and frequencies, compared to placebo. However, there was only a 20% reduction and that only appeared after 3 weeks. A randomized trial assessing the efficacy of both venlafaxine, a serotonin-norepinephrine reuptake inhibitor (SNRI), and soy protein revealed that neither agent was effective at reducing hot flashes in men with prostate cancer.[19] This result is notable because venlafaxine has been shown, in multiple randomized studies, to improve hot flashes in women [20, 21], thus demonstrating the importance of investigating gender-specific responses to interventions for managing hot flashes. While there are evidence-based options for treating male hot flashes, further study is warranted to identify additional interventions that provide both providers and patients with more effective means of hot flash management, with tolerable side effects.

#### **1.2** Oxybutynin for Hot Flashes

Oxybutynin is an anti-cholinergic agent which is available in both oral and transdermal formulations. Currently, oxybutynin is approved by the Food and Drug Administration (FDA) for use in managing overactive bladder symptoms. Additionally there are randomized trial data supporting off label use for the management of hyperhidrosis, with studies showing that this effect is equal across both genders.[22-24] Oxybutynin has a very good safety profile, with the most common reported adverse effects being xerostomia, drowsiness, dizziness, mild cognitive effects, and urinary retention, which are typically mild in severity and resolve with discontinuation, if not tolerable.[25]

In 2007, a manuscript reported retrospective data that supported the efficacy of oxybutynin for managing refractory hot flash symptoms in 52 cancer patients, including four men with ADT-

induced hot flashes.[26] The promising results of this study, which suggested a 70% response rate to oxybutynin with acceptable toxicity, led to the development of Phase III, double-blind, randomized trials comparing oxybutynin to placebo in women with hot flashes.[27, 28] One such trial demonstrated that moderate doses of oxybutynin substantially decreased hot flashes with mild to moderate toxicity. [27] More recently, our group completed another study which compared oxybutynin at doses of 2.5 and 5.0 mg BID to placebo in women with symptomatic hot flashes. These results were presented as an oral abstract at the 2018 San Antonio Breast Cancer Symposium, and showed that hot flash scores were significantly reduced from baseline in both the 2.5 mg (-10.6, SD 7.7) and 5.0 mg (-16.9, SD 15.6) treatment arms compared to placebo (-5.7, SD 10.2). Additionally, hot flash frequency was significantly improved for patients receiving both dose levels of oxybutynin (2.5 mg=60% reduction, 5.0 mg=77% reduction) over those treated with placebo (27% reduction). Reported treatment-related adverse effects for participants were typically mild and there was no difference in the discontinuation of the study drug between the oxybutynin and placebo arms. [28]

Additionally, a recent letter to the editor in the *New England Journal of Medicine* highlighted a case study of a man with hot flashes related to ADT which were refractory to high doses of gabapentin and venlafaxine, who then experienced a dramatic improvement after starting oxybutynin 2.5 mg twice daily.[29] Furthermore, members of our study team have anecdotally noted positive effects on hot flash symptoms when prescribing oxybutynin to manage urinary symptoms in men with prostate cancer. These observations, coupled with the positive effect of oxybutynin on hot flashes in women, support the conduct of a double-blind, placebo-controlled trial of oxybutynin for the management of hot flashes in men receiving ADT with a primary endpoint assessing the change in hot flash scores from baseline.

#### 1.3 Study Design

#### **1.3.1 Baseline period:**

We will utilize a one week period to obtain data regarding baseline hot flashes.

#### **1.3.2** Hot flash measurement

Patient reported outcome (PRO) measurements will be used as per the methodology that we described 18 years ago, [30] and that has also been used in trials conducted by other investigators. The primary endpoint of this study will assess the effects of the study interventions on patient reported hot flash scores. The calculation of this metric is defined in Section 2.1.1. Definitions of hot flash severity in men will be provided, based on data we collected from male patients who participated in a previous hot flash trial, and published 25 years ago.[31] Previous studies for hot flashes in men have utilized the same outcome measures to assess the study drug's efficacy and the hot flash score represents an ideal tool for quantitating multiple aspects of hot flash symptomatology.[12, 18, 30-32] We plan to use the Hot Flash Related Daily Interference Scale (HFRDIS), a tool developed by [name].[33] We recently assessed face validity by asking 10 men with androgen deprivation hot flashes to review this tool. All of the HFRDIS items were assessed as clear, appropriate, and easy to interpret. The items related to work and sexuality were identified as potentially difficult to answer if the individual was retired or not sexually active, however all of the men were able to provide a numeric score for these items. We also discussed the above with [name], who developed the HFRDIS tool and have identified other studies that have used the HFRDIS in men receiving androgen deprivation therapy.[34-36] These studies provide additional data supporting the reliability and validity of the 10-item instrument in this population. For example, Gonzalez, et al., (2015) provided evidence of construct validity in this population by demonstrating significant differences in scores between men receiving androgen deprivation therapy and men who only undergo

prostatectomy. [34] Beer, et al. (2010) demonstrated decreasing scores on both the HFD and HFRDIS following acupuncture in men undergoing androgen deprivation therapy, supporting concurrent validity of the HFRDIS [34].

#### **1.3.4** Cognitive effects

One potential concern when using anti-cholinergic agents, such as oxybutynin, for extended periods is the potential negative impact on cognition via interaction with muscarinic receptors within the central nervous system. Prospective studies, conducted primarily in elderly patients with overactive bladder symptoms, have demonstrated conflicting findings with regard to the effects of oxybutynin on neuro-cognition relative to placebo.[37-40] Questions relating to patient-reported cognition will be asked via the Symptom Experience Questionnaire (Appendix V) at baseline and weekly during the 6-week treatment period to help ascertain the effects of oxybutynin relative to placebo. These data will ultimately provide insight regarding the potential for cognitive toxicity with oxybutynin, which can be useful when considering the therapeutic index of this medication for treating hot flashes.

#### 2.0 **OBJECTIVES**

#### 2.1 Primary objective

2.1.1 To assess the effects of two doses of oxybutynin on hot flash scores (determined by multiplying the frequency of each defined hot flash grade by the severity [grade 0: none, 1: mild, 2: moderate, 3: severe, and 4: very severe] and summing the values over a 24-hour period) relative to placebo.

#### 2.2 Secondary objectives

- **2.2.1** To assess study accrual rates and compliance with the therapy.
- **2.2.2** To characterize the safety and adverse event profile of two doses of oxybutynin in the study population.
- **2.2.3** To evaluate the consistency of the results across the various methods used to evaluate the efficacy of oxybutynin (i.e., hot flash scores versus hot flash frequencies, mean differences versus 50% or greater reduction since baseline, single day versus full week to define patients' baseline hot flash scores).
- **2.2.4** To compare patient-reported quality of life and hot flash interference, as measured by the HFRDIS, across arms.
- **2.2.5** To compare other changes in patient symptoms, as measured by the Symptom Experience Questionnaire, across arms.

#### **3.0 PATIENT SELECTION**

For questions regarding eligibility criteria, see the Study Resources page. Please note that the Study Chair cannot grant waivers to eligibility requirements.

#### 3.1 On-Study Guidelines

This clinical trial can fulfill its objectives only if patients appropriate for this trial are enrolled. All relevant medical and other considerations should be taken into account when deciding whether this protocol is appropriate for a particular patient. Physicians should consider the risks and benefits of any therapy, and therefore only enroll patients for whom this treatment is appropriate.

Physicians should consider whether any of the following may render the patient inappropriate for this protocol:

- Psychiatric illness which would prevent the patient from giving informed consent.
- Medical condition such as uncontrolled infection (including HIV), uncontrolled diabetes mellitus or cardiac disease which, in the opinion of the treating physician, would make this protocol unreasonably hazardous for the patient.

#### 3.2 Eligibility Criteria

Use the spaces provided to confirm a patient's eligibility by indicating Yes or No as appropriate. It is not required to complete or submit the following page(s).

When calculating days of tests and measurements, the day a test or measurement is done is considered Day 0. Therefore, if a test were done on a Monday, the Monday one week later would be considered Day 7.

- **3.2.1** Men who are currently receiving androgen deprivation therapy (ADT) for the treatment of prostate cancer. ADT is defined by a history of orchiectomy, or ongoing usage of gonadotropin-releasing hormone agonists or antagonists. Men receiving abiraterone, but not enzalutamide, apalutamide, and darolutamide are eligible, as the latter three are metabolized by CYP3A4 and may affect oxybutynin serum concentrations.
- **3.2.2** Patients must be on a stable dose of all hormone-directed therapies for at least 28 days prior to registration and must not be planning to discontinue this therapy for at least 42 days following registration.

Patients receiving radiation therapy during the study period are eligible.

- 3.2.3 Eligible patient must have bothersome hot flashes for  $\geq$  14 days prior to registration, defined by an occurrence of  $\geq$  28 times per week and of sufficient severity to cause the patient to seek therapeutic intervention.
- 3.2.4 No current use or future planned use of any of the following agents during the study period: drugs that are not FDA approved for use in humans, drugs with category X interactions with oxybutynin [e.g. other anti-cholinergic agents, eluoxadloline, and potassium chloride], androgens, estrogens, progesterone analogs, gabapentin, cholinergic agonists, cholinesterase inhibitors, or complementary/alternative medicine taken for the purpose of managing hot flashes. No current or future planned use of strong CYP3A4 inhibitors (e.g. antipsychotic agents or macrolide antibiotics) during the study.

Prior use of these agents is permitted as long as they are discontinued before registration.

3.2.5 No current or prior use of oxybutynin for the treatment of hot flashes. Prior use of oxybutynin for other purposes (e.g. bladder symptoms) is allowed, as long as the patient has not taken any oxybutynin for 30 days prior to registration.

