#### 4.5.2 Treatment Assignments

The factors defined in Section 4.5.1 will be used as stratification factors.

After the patient has been registered into the study, the values of the stratification factors will be recorded, and the patient will be assigned to one of the following treatment groups using the Pocock and Simon dynamic allocation procedure [41] which balances the marginal distributions of the stratification factors between the treatment groups.

- Oxybutynin: 2.5 mL oral BID Days 8 through 49 (total of 42 days)
- Oxybutynin: 5 mL oral BID Days 8 through 49 (total of 42 days)
- Placebo: 2.5 mL oral BID Days 8 through 49 (total of 42 days)
- Placebo: 5 mL oral BID Days 8 through 49 (total of 42 days)

Note: Oxybutynin concentration = 1mg/mL.

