#### 7.1 Baseline Symptom Documentation

The patient will be instructed not to take any study medication for the first seven days of the study, but to complete their daily questionnaires (Baseline Symptom Documentation – Appendix II) during this baseline period. At the end of the week, patients will complete Symptom Experience Questionnaire (Appendix V) and Hot Flash Related Daily Interference Scale (Appendix VI).

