#### 8.0 DOSE AND TREATMENT MODIFICATIONS, UNBLINDING

#### 8.1 Ancillary Therapy, Concomitant Medications, and Supportive Care

- **8.1.1** Patients should not receive any other treatment or participate in trials which would be considered treatment for hot flashes or impact the primary endpoint. Simultaneous enrollment on other treatment studies is not allowed during the 7 week study period.
- **8.1.2** Patients should receive full supportive care while on this study. This includes blood product support, antibiotic treatment, and treatment of other newly diagnosed or concurrent medical conditions. All blood products and concomitant medications such as antidiarrheals, analgesics, and/or antiemetics received from the first day of study treatment administration until 30 days after the final dose will be recorded in the medical records.
- **8.1.3** Treatment of the patient's cancer should not be influenced by this study. If the patient stops ADT while participating in the study, it should be recorded on the study forms.

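### The entry rule against planned stopping of hormone therapy runs 42 days from registration, so it ends 6 to 7 days before blinded treatment does and misses nearly all of treatment Week 6

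*Combined protocol and SAP*

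**What the plan says.** Section 3.2.2 looks back and forward from registration. Looking back, it says: "Patients must be on a stable dose of all hormone-directed therapies for at least 28 days prior to registration". Looking forward, the patient "must not be planning to discontinue this therapy for at least 42 days following registration". The forward part concerns plans to stop; it does not mention dose changes, switches or additions.

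The schedule is longer than that window. Section 11.1 places the baseline diary after registration and randomization, and Section 7.1 states: "The patient will be instructed not to take any study medication for the first seven days of the study". Section 4.5.2 gives the treatment period, for example "Oxybutynin: 2.5 mL oral BID Days 8 through 49 (total of 42 days". Section 7.0 has treatment begin within 8 days of registration. Section 8.1.1 uses the full span: "Simultaneous enrollment on other treatment studies is not allowed during the 7 week study period". Footnote B of the Section 5.0 calendar equates treatment Week 6 with Week 7 from registration.

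On hormone agents, Section 3.2.1 admits men receiving abiraterone but not enzalutamide, apalutamide or darolutamide, because "the latter three are metabolized by CYP3A4 and may affect oxybutynin serum concentrations". Section 3.2.4 bars planned androgens, estrogens and progesterone analogs over the study period. Section 8.1.1 asks that patients not receive other treatment that would bear on the primary endpoint. Section 8.1.3 asks that the study not influence cancer treatment, and adds: "If the patient stops ADT while participating in the study, it should be recorded on the study forms".

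**The concern.** The forward part of 3.2.2 should keep the cause of the hot flashes steady while the drug is tested. Its 42 days equal the length of treatment but are counted from registration. This suggests that the baseline week was not added, although the documents do not say so. A man whose ADT is due to stop on Day 44 meets the criterion on either way of counting, and his Week 6 diary would then straddle the stop.

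The stability requirement also looks only backward. A planned change of GnRH agent, or a planned start of abiraterone or of one of the three agents excluded at entry, is not expressly addressed by any eligibility item. By the protocol's own reasoning in 3.2.1, starting one of those three could alter oxybutynin exposure. That can happen only in men taking oxybutynin, so the placebo comparison would not remove it.

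At stake is the cleanness of the last modelled week in a trial with 26 evaluable men per compared group. Section 13.4 names no analysis that deals with changes in hormone therapy.

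**Working it through.** **The plan's own figure.** Treatment on Days 8 to 49 is 49 − 8 + 1 = 42 days, as stated. Treatment Week 6 starts on Day 8 + 35 = 43 and ends on Day 49.

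**Where the 42-day window ends.** Section 3.2 gives a counting rule for tests and measurements, "the day a test or measurement is done is considered Day 0", but does not expressly apply it to registration. Both counts are shown.

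| | Registration = Day 0 | Registration = Day 1 |
|---|---|---|
| Window ends | 0 + 42 = Day 42 | 1 + 42 = Day 43 |
| Treatment days covered | 42 − 8 + 1 = 35 of 42 | 43 − 8 + 1 = 36 of 42 |
| Shortfall to Day 49 | 7 days | 6 days |
| Week 6 days uncovered | 7 of 7 | 6 of 7 |

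Counting from the first dose agrees. A start 8 days after registration, the latest allowed, puts the last dose at 8 + 41 = 49 days after registration, a 7-day shortfall. A start at 7 days puts it at 48, a 6-day shortfall.

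**Which week is the primary time point.** Sections 12.3.2, 13.1 and 13.4 count six weeks from randomization. Taken literally, that is about Day 42: inside the window, but after only 42 − 7 = 35 days of drug. Against this, the Section 13.4 model uses baseline plus weekly scores over the six treatment weeks. Section 4.7 ties the primary endpoint to questionnaires from men who have finished six weeks of treatment. The calendar runs to Week 7 from registration. Treatment Week 6 is the better reading. Even on the literal one, the last modelled week and the Day 49 HFRDIS fall after the window.

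**Illustrative size.** The documents give no rate of hormone-therapy change and no resulting score shift, so the shift is an assumption. Section 13.5 gives 26 men per oxybutynin arm and 13 + 13 = 26 on pooled placebo. Section 1.2 gives mean reductions of 16.9 (5.0 mg), 10.6 (2.5 mg) and 5.7 (placebo) in the trial in women. The differences are 16.9 − 5.7 = 11.2 and 10.6 − 5.7 = 4.9. The arm mean moves by (men × shift)/26.

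| Assumed shift | Move in arm mean | % of 11.2 | % of 4.9 |
|---|---|---|---|
| 1 man, 5 points | 5/26 = 0.19 | 1.7% | 3.9% |
| 1 man, 10 points | 10/26 = 0.38 | 3.4% | 8% |
| 2 men, 10 points | 20/26 = 0.77 | 6.9% | 16% |

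For scale, the SDs in Section 1.2 (7.7 low dose, 10.2 placebo) with 26 per group give a standard error for the low-dose difference of √((7.7² + 10.2²)/26) = √(163.33/26) = 2.5. One man shifting by 10 points is 0.38/2.5, about 15% of one standard error.

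**The case against.** The best defence is that the criterion governs only plans at entry, that such plans are fixed before randomization, and that a blinded intent-to-treat comparison balances the resulting changes on average. Men with orchiectomy cannot stop ADT at all. For a late stop to matter, the score must also move within at most 7 days, and the documents give no basis for that speed. This stands, and it makes the main harm noise rather than bias. The possible exception is altered oxybutynin exposure, whose frequency and direction are not given.

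Three stronger readings are tempting but unsupported.

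- A reader might infer that planned starts of new hormone agents are simply allowed. Section 3.2.4 bars androgens, estrogens and progesterone analogs, and 8.1.1 discourages treatment that would bear on the primary endpoint. What remains is a gap for the agents named above, with 8.1.1 and 8.1.3 pulling in different directions. That is a matter to reconcile, not a permission.
- A reader might infer that only stopping is recorded. Appendix VII has staff document changes in medications or other treatments at each weekly call, and 8.1.2 has concomitant medications kept in the medical records. The remaining gaps are exact dates and any planned use of these data in the analysis.
- A reader might state flatly that the whole primary-endpoint week is uncovered. That depends on counting registration as Day 0 and on reading the endpoint as treatment Week 6.

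**Conclusion.** The concern holds in a limited form. The no-stop window in 3.2.2 ends 6 to 7 days before the end of blinded treatment and leaves 6 to 7 of the 7 days of treatment Week 6 uncovered. This follows from the schedule alone. That these days form the primary-endpoint week rests on the better, but not the only, reading of the time point.

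The wording gap on planned changes of GnRH therapy, and on planned starts of abiraterone or the three excluded agents, is also real.

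The likely impact is modest. The percentages above rest on an assumed shift in an assumed number of men, and on effects seen in women. The smaller percentage belongs to the high-dose comparison, which Section 13.4 tests first. The stated power and sample size are unaffected.

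**What to change.** 1. In 3.2.2, run the entry-plan window through study Day 49, the last day of blinded treatment, instead of 42 days from registration. Naming the study day also removes the Day 0 or Day 1 ambiguity.
2. Reconcile 3.2.1, 3.2.2, 3.2.4, 8.1.1 and 8.1.3 so that they say one thing about planned starts, switches or dose changes of hormone-directed therapy. What that rule should be is for the sponsor to decide.
3. Reconcile the primary time point across Sections 4.7, 5.0, 12.3.2, 13.1 and 13.4, so that it is clear whether six weeks runs from randomization or from the start of treatment.
4. Use the medication changes already documented at the weekly calls, adding dates. Specify a sensitivity analysis that omits hot flash scores recorded after a hormone-therapy change, alongside the intent-to-treat analysis and not in place of it.

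The cost is a few words of eligibility text, one date field and one extra model run. No extra patients are needed, and the window change leaves cancer care alone because it concerns plans at entry. The downside is that some men with a planned change in the window are deferred; the documents do not let us say how many.
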